7. RATIONALE AND BACKGROUND

Prostate cancer (PC) is the most common cancer and the second leading cause of cancer death among men in the United States.¹ The National Cancer Institute (NCI) estimated 299,010 new cases and 35,250 deaths of PC in 2024.² While the long-term outlook is positive for early-stage PC, survival rates drastically decrease once the disease has spread beyond the prostate gland (i.e., becoming metastatic) or when the disease becomes castration-resistant.²

Androgen deprivation therapy (ADT) is the standard of care for patients with PC, including such as injectable luteinizing hormone-releasing hormone (LHRH) agonists (e.g., leuprolide) and gonadotropin-releasing hormone (GnRH) antagonist. ADT treatment can suppress testosterone level to castrate level and delay the progression of the disease. LHRH agonist use can cause an initial surge of testosterone which results in a flare of symptoms including bone pain or obstructive urinary symptoms. In addition, LHRH agonist is associated with an increased risk of cardiovascular events.³ As an alternative to LHRH, GnRH antagonist can be considered, which does not cause the initial surge in testosterone level.

Relugolix is a recently approved GnRH antagonist, which can rapidly suppress testosterone level without the initial surge. The phase 3 HERO trial of relugolix in advanced PC patients has compared the efficacy and safety of oral relugolix with leuprolide and has found that relugolix can achieve castration quicker and can better maintain castration than leuprolide.⁴ In addition, the incidence of major adverse cardiovascular events in the HERO trial was also lower for relugolix than leuprolide (2.9% vs. 6.2%).⁴ The positive results have led to the Food and Drug Administration (FDA) approval of relugolix in December 2020.⁵

Relugolix is the only ADT option available in oral form, distinguishing from the traditional injectable LHRH agonists.⁶ While many factors could influence patients' treatment preferences, a

¹ American Cancer Society (ACS), the Centers for Disease Control and Prevention (CDC), the North American Association of Central Cancer Registries (NAACCR), and the NCI. Annual Report to the Nation 2022. https://seer.cancer.gov/report_to_nation. Accessed on May 1, 2023.

² NCI. Cancer Stat Facts: Prostate Cancer. <https://seer.cancer.gov/statfacts/html/prost.html>. Accessed on May 1, 2023.

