9. RESEARCH METHODS

9.1. Study design

This is a retrospective, observational study using January 1, 2006 – December 31, 2023 data from the National VA Health Care Network databases. PC patients who initiated relugolix will be selected based on diagnosis codes, age, treatment received, and continuous activity in the health care network. The identification period for relugolix use will be from December 18, 2020 to December 31, 2023. December 18, 2020 is the approval date for relugolix in the US, and December 31, 2023 is the end of available data. The index date will be defined as the initiation date of relugolix. The baseline period will be 365 days prior to the index date (hence the start of the study period is December 18, 2019). The follow-up period will be from the index date to the earliest of death, end of continuous eligibility or end of data availability. Most of the patient characteristics will be described during the baseline period. Certain patient characteristics will be described using all data available prior to the index date (i.e., data prior to December 18, 2019 will also be used if available; see more details in Table 2). Treatment patterns, adherence, and persistence with relugolix, and PSA and testosterone responses (if sample size allows) will be assessed during the follow-up period.

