Comorbidities	A binary variable (yes/no) will be created for patients with a diagnosis of each of the following comorbidities during the baseline period: 
• Hypertension• Hyperlipidemia• Diabetes• Urinary tract infection• Chronic obstructive pulmonary disease• Arrhythmia• Congestive heart failure• Myocardial infarction• Stroke• Angina pectoris• Inflammatory bowel disease• Acute coronary syndrome• Sexual dysfunction• Depression• Anxiety• Hot flashes• Cognitive impairment• Major adverse cardiovascula event (defined by any evidence of cardiomyopathy, heart failure, ischemic heart disease, myocardial infarction, pulmonary embolism, or stroke)
PSA	Baseline PSA value (among available) based on the PSA value closest to the index date during the 90-day window (or 180-day, to be finalized based on the number of patients with non-missing PSA value in these time frames) on or prior to the index date will be evaluated.
Testosterone	Baseline testosterone value (among available) based on testosterone value closest to the index date during the 90-day window (or 180-day; will be consistent with the time window for baseline PSA) on or prior to the index date will be evaluated.
Metastatic vs. non-metastatic PC	A binary variable for patients with metastatic vs. non-metastatic PC will be created. Metastatic PC will be

Variable	Operational definition
	defined as having evidence of metastasis during the baseline period or within 90 days since the index date.
ADT naïve vs. ADT experienced	A binary variable for patients who were ADT naïve vs. ADT experienced will be created. ADT naïve will be defined as having no records of any systemic ADT treatment ever based on all available data prior to the index date (i.e., including baseline period data and any available data prior to the baseline period). Systemic ADT treatment includes LHRH agonists and GnRH antagonists (i.e., degarelix, relugolix, goserelin, histrelin, leuprolide, triptorelin)

Table 3. Treatment patterns, adherence, persistence, and clinical variables during the follow-up period

Variable	Operational definition

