	divided by a pre-determined period following treatment initiation (e.g., 6 and 12 months) Adherence will be described as a continuous variable and as a binary variable (<0.80: non-adherent, ≥ 0.80 : adherent)
Treatment persistence	Persistence to relugolix will be described as the proportion of patients who did not discontinue relugolix (i.e., with a treatment gap, switch to another ADT, or death; the minimum days of treatment gap, e.g., 45 or 60 days, will be finalized based on sample size and clinical input) during the follow-up period. Treatment gaps will be assessed from the end of the days of supply of the previous prescription to the earliest of the next prescription or the end of data availability.
PSA response	Only if sample size is sufficient and among patients with at least one baseline and one follow-up period PSA measure: 
• The number and percentage of patients with $\geq 50\%$ and $\geq 90\%$ decline from the baseline PSA to any PSA measurement during the follow-up period and while on relugolix• The number and percentage of patients with the nadir PSA value during the follow-up period and on treatment of relugolix < 0.01, 0.1, and 0.2 ng/mL
Testosterone response	Only if sample size is sufficient and among patients with at least one follow-up period testosterone measure: 
• The number and percentage of patients with at least one testosterone value of <50ng/dL and <20 ng/dL during the follow-up period and while on relugolix 
If sample size is sufficient, the analysis above may be conducted among patients with at least one baseline and one follow-up period testosterone measure

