9.7.2.3. Time to treatment changes

Kaplan-Meier analysis will be conducted to describe the following time-to-event outcomes for the treatment patterns as listed in [Table 3](#):

PFIZER CONFIDENTIAL

- Time to discontinuation of relugolix
- Time to switching to a different ADT treatment
- Time to add a new systemic PC treatment to relugolix

The number and proportion of patients with the corresponding event will be plotted over time and the number at risk table over time will be presented. The median time to event will be calculated.

9.7.3. Data analysis for Objective 3: To estimate adherence and persistence with relugolix among patients with PC who initiated relugolix

Adherence to relugolix as defined in [Table 3](#) will be described. MPR will be summarized over the entire exposure to relugolix during the follow-up period. PDC will be summarized within the 6, 12, and 18 months (tentatively, pending on the final length of follow-up) since the index date. Means, standard deviations, medians, and interquartile range will be estimated for adherence as a continuous variable. Counts and percentages will be estimated for adherence as a binary variable. Patients will be required to have complete follow-up data during the time to be included in each adherence calculation.

Persistence to relugolix as defined in [Table 3](#) will be described using Kaplan-Meier analysis since the index date. The number and proportion of patients persistent to relugolix will be plotted over time and the number at risk table over time will be presented.

9.7.4. Data analysis for Objective 4: To assess testosterone suppression and PSA responses among ADT naïve patients with PC who initiated relugolix

If sample size is sufficient, the count and percentage of patients with testosterone responses as defined in [Table 3](#) will be calculated among ADT naïve patients with at least one testosterone measure during the follow-up period. Similarly, if sample size is sufficient, the count and percentage of patients with PSA responses as defined in [Table 3](#) will be calculated among ADT naïve patients with at least one baseline and one follow-up period PSA measure.

9.7.5. Data analysis for Objective 5: To describe and compare demographics and clinical characteristics between Black and non-Hispanic White patients with PC who initiated relugolix

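### PSA and testosterone response: day 0 lies in both the baseline and follow-up windows, the denominators do not require an on-treatment value, and the testosterone rule records only whether suppression was ever reached

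*Combined protocol and SAP*

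**What the plan says.** Section 9.1 fixes day 0: "The index date will be defined as the initiation date of relugolix". It then starts follow-up on that day: "The follow-up period will be from the index date to the earliest of death, end of continuous eligibility or end of data availability". Section 9.2.1 defines follow-up in the same way.

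Table 2 in Section 9.3 takes baseline PSA as the value nearest to index in a 90-day (or 180-day) window: "non-missing PSA value in these time frames) on or prior to the index date will be evaluated". Baseline testosterone follows the same window: "will be consistent with the time window for baseline PSA) on or prior to the index date will be evaluated".

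In Table 3, the testosterone numerator is the number of men with "at least one testosterone value of <50ng/dL and <20 ng/dL during the follow-up period and while on relugolix". The PSA numerators are a decline of at least 50% or 90% from baseline to any follow-up PSA taken on relugolix, and an on-treatment nadir below 0.01, 0.1 or 0.2 ng/mL.

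The denominators are wider. Section 9.7.4 computes testosterone response in "ADT naïve patients with at least one testosterone measure during the follow-up period". For PSA it asks for one baseline and one follow-up measure. Neither denominator mentions being on relugolix. Both analyses run only if the sample size is sufficient.

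**The concern.** There are two separate issues.

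The first is who is counted. A sample drawn on the day relugolix starts is in substance a pre-treatment sample, yet it meets the definition of a follow-up value. A sample drawn after relugolix has stopped also meets the denominator condition but can never meet the numerator condition. Men with only such values add to the denominator without carrying any information on response to the drug.

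The second is what is counted. One on-treatment value below the cut-off is enough, however many tests were done and whatever the later values show. The background in Section 7 says of the phase 3 trial that it "has found that relugolix can achieve castration quicker and can better maintain castration than leuprolide". A reader may take the reported percentage to bear on maintenance as well, and it cannot.

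At stake are the percentages reported for Objective 4, and whether two programmers working from the same text would produce the same ones.

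**Working it through.** The documents state no response rate, sample size or testing frequency for this objective, so there is no figure to reproduce. Steps 1 and 2 rest on the text alone. Steps 3 to 5 use assumed inputs.

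**1. Window boundaries.** The baseline laboratory window ends on day 0, inclusive. Follow-up begins on day 0, inclusive. The overlap is exactly one day, and no rule assigns a day-0 sample to one side. The overlap is peculiar to the laboratory variables: the general baseline period is the 365 days before index, and adherence is described after index.

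**2. Numerator against denominator.**

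| Follow-up values available | In denominator? | How the man is scored |
|---|---|---|
| Day 0 only | Yes. For PSA, the one sample can meet both conditions | PSA decline: 0% by construction, because the value nearest to index is that same sample. Nadir and testosterone: non-response, unless the value is already low and day 0 is read as on relugolix |
| After discontinuation only | Yes (for PSA, if a baseline exists) | Non-response on every measure, because no value is on treatment |
| Day 0 plus later on-treatment values | Yes | Decided by the later values, except that an already low day-0 value could add a nadir or testosterone success |

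The on-relugolix condition does not settle the first row. Its first day is not defined for laboratory dates, and day 0 is the initiation date.

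**3. Size of the dilution.** Let R be the true response rate, f the share of the denominator with no usable on-treatment value, and q the chance that such a man is nevertheless scored as a responder. Reported rate = (1 − f) × R + f × q. Take R = 0.90:

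- q = 0: f = 5% gives 0.95 × 0.90 = 85.5%; f = 10% gives 0.90 × 0.90 = 81%; f = 20% gives 0.80 × 0.90 = 72%.
- q = 0.30: 87%, 84% and 78% for the same shares.
- f = 0: 90%, so no bias.

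For PSA decline on a day-0-only sample, and for men with only post-discontinuation values, q = 0 by definition. For testosterone and nadir on day 0, q is unknown.

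**4. Ever rule and number of tests.** Suppose each on-treatment value is below the cut-off with probability p = 0.80. If values within a man are independent, the ever rule gives 1 − 0.20^k and an all-values rule gives 0.80^k:

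| Tests per man (k) | Ever below | All below |
|---|---|---|
| 1 | 80% | 80% |
| 2 | 96% | 64% |
| 3 | 99.2% | 51.2% |

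If values within a man are perfectly correlated, both rules give 80% at every k. Real data lie in between. What does not depend on the correlation is that another test can never turn an ever-responder into a non-responder.

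**5. Loss of suppression.** If 95% of men ever reach the cut-off and 0%, 10%, 20% or 30% of them later lose suppression, the planned measure reads 95% each time. The sustained rate is 0.95 × (1 − e), that is 95%, 85.5%, 76% or 66.5%.

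**The case against.** The best defence of the first issue is that it is an edge case. Under an any-value or nadir rule, a day-0 value cannot harm a man who also has a responding on-treatment value, so only men with no usable later value are affected downwards. Entry requires two prescriptions and 90 days of activity unless the man died, which leaves time for a later test. One baseline and one follow-up PSA also reads most naturally as two samples. This limits the likely size, which the documents do not give. It does not remove the overlap, and it does not touch the mismatch between an on-treatment numerator and an any-follow-up denominator.

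On the second issue, an ever-achieved response is a legitimate summary. No passage promises sustained castration as an endpoint, and the background also cites speed of castration, absence of a surge, cardiovascular events and the oral route. That stands: the rule is not an error, but it needs its proper label and a companion summary.

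A reader might infer that the overlap inflates results by scoring pre-treatment values as successes. The text does not support that as the main effect. These men are ADT-naïve and prior bilateral orchiectomy is excluded, so a day-0 testosterone would be expected to be mostly above the cut-off (an assumption), and a day-0 PSA gives 0% decline. The exception is a PSA already low on day 0, for example after prostatectomy, which is not excluded; it could count as a nadir success.

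**Conclusion.** The point holds in a limited form. As written, the plan lets one day-0 PSA act as both baseline and follow-up. It also places men with only day-0 or post-discontinuation values in the denominator, mostly as non-responders. The direction is downward. The size cannot be estimated from the documents, and the figures in step 3 show only how it scales with an assumed share. Separately, the testosterone measure cannot fall with more tests or longer on-treatment follow-up, and it cannot show loss of suppression.

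It would go too far to infer that the percentages will reflect test timing and frequency more than drug effect. The two effects run in opposite directions, neither is quantified, and the steep contrast in step 4 depends on independent tests.

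Objective 4 is exploratory, has no comparator and runs only if numbers allow; the primary objective is unaffected. This is a modest correction, worth making before the analysis is programmed.

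**What to change.** In Table 3 and Section 9.7.4:

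- Start the PSA and testosterone response window after the index date, so that a day-0 sample can serve only as baseline.
- Require for the denominator at least one on-treatment value in that window, from a different sample than baseline. State how on-treatment status is determined for a laboratory date.
- Label the existing testosterone measure as *ever achieved*.
- Add a descriptive testosterone summary in fixed windows from index, using the last on-treatment value in each window, with the number of men tested and the number of tests per man. Fixed periods already suit this plan: Section 9.7.3 tentatively uses 6, 12 and 18 months for PDC.
- If a line for all on-treatment values below 50 ng/dL is also reported, give the number of tests beside it. It depends on test frequency too, in the opposite direction (80% to 51.2% in step 4).

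The cost is a few sentences and one table. A few men leave the denominator, and each window holds fewer men than the whole follow-up period, which matters for an analysis that already depends on sample size.

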9.4. Data sources

January 1, 2006 to December 31, 2023 data from the National VA Health Care Network will be used for this study. This network is the US's largest integrated health care system with over 1,700 sites of care, serving approximately 8.76 million veterans each year. The VA Health System Corporate Data Warehouse (CDW) includes all medical encounter information in the VA, comprised of medical centers, community-based outpatient clinics, community-living centers, veteran centers, and domiciliaries. The VA CDW stores data in separate databases, one for each type of clinical information - inpatient medication, inpatient laboratory, inpatient admission, outpatient medication, outpatient laboratory, outpatient visits, etc. The databases provide demographic information and contain comprehensive services, including primary care, specialty care, inpatient care, rehabilitation, long-term care, home care, and other services, to military veterans. The database also includes date of death. The date of death is extracted from the VA electronic health record systems and verified by official sources, including VA facilities, death certificates, and National Cemetery Administration. Information on CDW, including date of death, is updated on a daily base. Cause of death is not available on CDW.

9.5. Study size

As no priori hypotheses are specified, sample size calculations are not applicable. The number of patients eligible for the study will be determined in accordance with the sample selection conducted per the criteria described in Section 9.2.

9.6. Data management

A clean, patient-level dataset will be generated for use throughout the study. This process will entail basic exploratory checks to ensure data integrity; cleaning and reformatting the raw data as needed; and creating variables for all key study measures, including patient characteristics, treatment start and end dates, and classification of treatments and medication. All data will be stored and maintained on a secure encrypted non-cloud-based server and accessed over a secure internal private wide area network. The data will be made accessible only to individuals working on the current study. No attempt will be made to identify individual patients, hospitals, or physicians. Analyses will be conducted using SAS 9.4 (SAS Institute, Cary NC).

9.7. Data analysis

9.7.1. Data analysis for Objective 1: To describe demographics and clinical characteristics of patients with PC who initiated relugolix

Descriptive analysis will be conducted for baseline demographics and clinical characteristics. Means, standard deviations, medians, and interquartile range will be estimated for continuous variables. Counts and percentages will be estimated for categorical variables. If the sample sizes allow, standardized mean difference (SMD) will be calculated to compare the patient baseline characteristics between metastatic vs. non-metastatic PC cohorts. For each variable, the SMD will be calculated as the difference in mean between two cohorts divided by the standard

deviation of the two cohorts pooled together. The absolute value of a SMD $> 10\%$ will be considered as an indicator for significant imbalance.

9.7.2. Data analysis for Objective 2: To assess treatment patterns among patients with PC who initiated relugolix

[figure not shown]
9.7.2.1. Index treatment distribution

The distribution of the index treatment will be described using counts and percentages. Index treatment will be defined based on treatments received within 30 days before the index date and within 90 days after the index date.

9.7.2.2. Treatment patterns of relugolix

Treatment patterns of relugolix will be analyzed and presented using Sankey diagrams (see an example in Figure 2). The four treatment patterns described in [Table 3](#) will be considered. The number and proportion of patients with each of the four treatment patterns will be summarized.

Figure 2. Example of a Sankey diagram (for illustration purpose)

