9.2.1. Inclusion criteria

Patients who met all of the following sample selection criteria will be included:

- Male with ≥ 1 diagnosis of PC (International Classification of Diseases, 10th Revision, Clinical Modification [ICD-10-CM] C61)
- Had ≥ 2 prescriptions of relugolix on or after the first observed PC diagnosis. The initiation date of relugolix will be selected as the **index date**
- At least ≥ 18 years old as of the index date
- Had continuous activity in the data for ≥ 365 days prior to the index date and ≥ 90 days since the index date (unless died within 90 days). The **baseline period** will be defined as the 365-day period prior to the index date. The **follow-up period** will be from the index date to the end of continuous eligibility, data availability, or death, whichever happened first

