Index treatment	
Index treatment regimens include:
 
 • Relugolix monotherapy • Relugolix + NSAA only (at least 90 days of NSAA use) • Relugolix + ARPI +/- NSAA (no chemotherapy) • Relugolix + ARPI + chemotherapy • Relugolix + chemotherapy +/- NSAA (no ARPI) • Relugolix + other (no ARPI, no chemotherapy) 
Index treatment regimen will be defined based on treatments received within 30 days before the index date and within 90 days after the index date.
 
Specific treatments included in each treatment category (i.e., ADT, NSAA, ARPI, chemotherapy, immunotherapy) are described in “Treatment history” in Table 2. Other treatments include immunotherapy, radium 223, olaparib, rucaparib, talazoparib, niraparib and lutetium Lu 177 vipivotide tetraxetan.
 
Number of patients who received any radiotherapy during the index treatment will be summarized.

Variable	Operational definition
Treatment patterns of relugolix	
Treatment patterns of relugolix include:
 
• Continued relugolix as in the index treatment (regardless of discontinuation of concomitant medications)• Continued relugolix with a new add-on systemic PC treatment (excluding ADT)• Discontinued relugolix and switched to another ADT treatment• Discontinued relugolix without switching to another ADT treatment 
Add-on systemic PC treatments include:
 
• ARPI• NSAA• Chemotherapy• Immunotherapy• Radium 223• Ketoconazole• Olaparib• Rucaparib• Talazoparib• Niraparib• Lutetium Lu 177 vipivotide tetraxetan 
Add-on therapy will be evaluated from 90 days after the index period to the end of the follow-up period.

Time to treatment changes	The time to treatment changes of interest include: 
• Time to discontinuation of relugolix• Time to switching to a different ADT treatment• Time to add a new systemic PC treatment to relugolix
Treatment adherence	Adherence to relugolix post the index date will be described using both MPR and PDC: 
• MPR: Sum of the days of supply divided by the number of days between the first fill and the end of the last refill (i.e., including the days of supply from the last refill)• PDC: Sum of the non-overlapping (i.e., not double counting of overlaps) days of supply covered

Variable	Operational definition

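### The four treatment-pattern proportions and the Sankey diagram have no common time point, so they mix relugolix use with length of observation

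*Combined protocol and SAP*

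**What the plan says.** Table 3 (section 9.3) defines four patterns: staying on relugolix as in the index treatment, staying on it with a new add-on, stopping with a switch to another ADT, and stopping without one. Section 9.7.2.2 presents them in Sankey diagrams and adds: "The number and proportion of patients with each of the four treatment patterns will be summarized". It names no time point, no minimum observation for a patient to be counted, and no handling of censoring.

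Section 9.1 sets the observation time:
- "The identification period for relugolix use will be from December 18, 2020 to December 31, 2023".
- "December 31, 2023 is the end of available data".
- "The follow-up period will be from the index date to the earliest of death, end of continuous eligibility or end of data availability".

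Section 9.2.1 asks for only 90 days of activity after the index date and waives this for patients who die earlier.

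Two definitions in Table 3 affect how soon a patient can leave the first pattern. For add-on: "Add-on therapy will be evaluated from 90 days after the index period to the end of the follow-up period". For discontinuation: "the minimum days of treatment gap, e.g., 45 or 60 days, will be finalized based on sample size and clinical input".

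Section 9.7.2.3 plans Kaplan-Meier analyses of time to stopping, time to ADT switch and time to add-on. Section 9.7.3 adds Kaplan-Meier persistence. For adherence, 9.7.3 uses PDC horizons of 6, 12 and 18 months (tentative) and admits only patients with complete follow-up for the calculation. The limitations in 9.9 do not mention unequal follow-up.

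**The concern.** A proportion taken over all available follow-up has no defined time scale when patients are observed for very different lengths. A man who started in early 2021 has almost three years in which to add, switch or stop. A man who started in late September 2023 has about three months, and is likely to be counted as continuing simply because the data end. Two cohorts with identical behaviour but different uptake curves would give different tables and different Sankey flows.

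Describing real-world treatment patterns is a stated aim of the study (section 7), and a four-way percentage split is easily quoted without its follow-up. A reader could not tell what period the figures describe, or set them beside figures from another data source.

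**Working it through.** The documents state no expected proportion, event rate, uptake curve or sample size, so there is no figure of the plan's to reproduce. The check takes the dates from the protocol and uses labelled assumptions for the rest.

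**1. Range of follow-up.** From 18 December 2020 to 31 December 2023 is 3 × 365 + 13 = 1,108 days, or 1,108 / 365.25 = 3.03 years (36.4 months). The latest index date that leaves 90 days is 2 October 2023 (29 + 30 + 31 = 90).

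**2. A patient with exactly 90 days.**
- Add-on: if the window is read as opening at day 90, this patient has no time at risk.
- Stopping by treatment gap: section 9.9 describes the two required prescriptions as a first and a second month. Assuming two 30-day fills taken back to back, supply ends at day 60. A 45- or 60-day gap then completes at day 105 or 120, after the data end. A long gap between the first and second fill could complete sooner.
- Switch to another ADT: this can be seen at any time.

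**3. Effect of accrual shape at a fixed hazard.** Assume a constant stopping hazard of 0.04 per month, censoring only at the data cut-off, and follow-up f between 3.0 and 36.4 months with entry weight w(f):

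crude stopped share = ∫ w(f) [1 − exp(−0.04 f)] df / ∫ w(f) df

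For uniform entry this is 1 − [exp(−0.12) − exp(−1.456)] / (0.04 × 33.4) = 1 − (0.8869 − 0.2332) / 1.336 = 51%.

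| Assumed accrual | w(f) | Crude stopped share |
|---|---|---|
| Front-loaded | f − 3.0 | 62% |
| Uniform | 1 | 51% |
| Linear growth | 36.4 − f | 40% |
| Steeper growth | (36.4 − f)² | 34% |

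The true risk is the same in every row: 1 − exp(−0.24) = 21.3% at 6 months, 1 − exp(−0.48) = 38.1% at 12 months and 1 − exp(−0.72) = 51.3% at 18 months. Against 12 months, the crude share is too high in three rows and too low in one. Against 18 months, uniform entry is about right and both growth rows are too low.

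**4. Second check, on days.** Assume a 30% 12-month risk and follow-up of 90 to 1,108 days. The chance of an observed event is 1 − 0.7^(90/365) = 8% for the shortest follow-up and 1 − 0.7^(1108/365) = 66% for the longest. The crude share is 32% with late-weighted entry, 42% with uniform and 51% with early-weighted. A simulated Kaplan-Meier estimate at 12 months (200,000 patients per case) is 29.8% to 30.0% in all three.

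**5. Drug use still matters.** With entry held uniform, the crude share rises from 30% to 63% as the assumed 12-month risk rises from 20% to 50%. That is 33 points. Moving from late- to early-weighted entry shifts it by 15 points at a 20% risk (22% to 37%) and 23 points at a 50% risk (51% to 74%).

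**6. What the planned curves cover.** There is a curve for all stopping, one for switching and one for add-on. None is for stopping without a switch. It cannot be had by subtracting the switch curve from the stopping curve, because the plan does not say how competing events are treated and separate curves need not add up. The four-way split at a common time is therefore not available elsewhere in the plan.

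**The case against.** The strongest reply is that censoring is handled in the very next section. Sections 9.7.2.3 and 9.7.3 give time-specific curves, with numbers at risk, for stopping, switching, add-on and persistence. Objective 2 is exploratory, and Table 1 lists the Sankey diagram and the Kaplan-Meier analyses as its endpoints, not the pattern proportions separately. All of this stands and limits the point to the four-way table and the Sankey. It does not remove it, because those outputs are planned and still have no time scale.

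A reader might also infer more than the documents support:
- *That the proportions show start date instead of drug use.* They show both (step 5).
- *That rising uptake makes the continuing share too favourable.* With linear growth in step 3, crude stopping is slightly above the 12-month risk (40% against 38.1%). The direction is not fixed.
- *That the race comparison is affected.* Section 9.7.6 repeats only 9.7.2.3 by race and 9.7.7 repeats 9.7.3. No comparison of these proportions by race is planned.
- *That this is the main result of Objective 2.* Table 1 does not rank it so.
- *That the four patterns must overlap.* A man who adds a drug and later stops fits two of them if they are read as events during follow-up. Read as status at the end of follow-up, they are exclusive. The protocol does not say which reading applies, and the example Sankey figure is not available to settle it.

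**Conclusion.** The point holds for the pattern proportions and the Sankey diagram in 9.7.2.2: they pool follow-up of 90 days (less after an early death) to 1,108 days with no common horizon. That part rests on the protocol's own dates and rules. The size is illustrative: about 34% to 62% crude stopping against a constant 38.1% at 12 months. It assumes a constant hazard of 0.04 per month, four accrual shapes and censoring at the data cut-off only. Other hazards or uptake curves would change the size and possibly the direction, but not the dependence on observation time. The consequence is modest, since the output is exploratory and descriptive, but the improvement is cheap and worth making.

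**What to change.** In section 9.7.2.2 and Table 3:

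1. Define the patterns as mutually exclusive status at a given time: on relugolix without add-on, on relugolix with add-on, stopped and switched ADT, stopped without a switch. Make death a separate state. Use status at each time in preference to first change only, so that later transitions stay visible in the Sankey. Settle the gap definition beforehand, and state how a restart is classed.
2. Report the share in each state, and draw the Sankey columns, at 6, 12 and 18 months, matching the PDC horizons in 9.7.3. Use a multi-state (Aalen-Johansen) estimate. Alternatively, use patients who died by that time or have complete follow-up to it, with deaths kept in the denominator. If the second route is taken, apply it among patients indexed early enough to reach that time before 31 December 2023. Otherwise late starters who die are counted while their surviving contemporaries are left out.
3. Report the distribution of follow-up beside the table, and label any all-follow-up proportions as crude.
4. Add unequal follow-up to the limitations in 9.9.

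The cost is protocol wording and some programming, with no new data. The downside is that later time points rest on fewer patients: a full 365 days needs an index date no later than 31 December 2022, and 548 days needs one no later than 1 July 2022.
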